12.2 Data Handling

Refer to **Table 12-1** for details on which PD and PK samples to be collected based on body weight at Visit 1 and Visit 2.

Table 12-1 PD (for efficacy) and PK Sampling Based on Body Weight

| Body weight at Visit 2 | Visit 2 | |
|------------------------|------------------------------|---|
| | PD samples to draw | PK samples to draw |
| BW > 10.0 kg | pre-dose 15 min 30 min | pre-dose 10 min 20 min 30 min 40 min 60 min 90 min 140 min 220 min 300 min |
| 10.0 ≥ BW > 9.0 kg | pre-dose 15 min 30 min | pre-dose 10 min 20 min 30 min 40 min 60 min 90 min 140 min 300 min |
| 9.0 ≥ BW > 8.0 kg | pre-dose 30 min | pre-dose 10 min 20 min 30 min 40 min 60 min 90 min 140 min 300 min |

Abbreviations: BW=body weight; PD=pharmacodynamics; PK=pharmacokinetics

The raw plasma concentration data will be handled as follows:

For summary tables and figures for plasma concentrations:

- i.) For all pre-dose samples, the sampling time will be set to zero.
- ii.) For post-dose samples, the planned sampling time will be used in summary tables, and the actual sampling times will be used for all figures of individual concentrations.
- iii.) All concentration values below the Limit of Quantification (BLOQ) will be set to zero.
- iv.) Missing post-dose values will not be replaced.

For determination of PK metrics:

- i.) For all pre-dose samples, the sampling time will be set to zero.
- ii.) For post-dose samples, the actual sampling time will be used.
- iii.) All pre-dose concentration values will be set to zero.
- iv.) Post-dose concentration values BLOQ after T_{max} will be set to missing.
- v.) Missing post-dose values will not be replaced.
- vi.) A concentration that is BLOQ is assigned a value of zero if it occurs in a profile after dosing at time zero and before the first measurable concentration.
- vii.) If a BLOQ value occurs after a measurable concentration in a profile and is followed by a value above the lower limit of quantification, then the BLOQ is treated as missing data, and the time point is ignored in the computations.
- viii.) If a BLOQ value occurs at the end of the collection interval (after the last quantifiable concentration) it is treated as missing data.
- ix.) If two BLOQ values occur in succession after C_{max} , the profile is deemed to have terminated at the first BLOQ value and any subsequent concentrations and time points are omitted from pharmacokinetic calculations.

12.3 Presentation of Plasma Concentrations

Individual plasma concentration results:

A raw data listing will be provided displaying the dasiglucagon concentration as reported and nominal and actual sampling times relative to the start dose of study drug. Results will be displayed using 3 significant digits.

Summary statistics of plasma concentrations:

The dasiglucagon plasma concentrations will be summarized using descriptive statistics (n, arithmetic mean, SD, coefficient of variation (CV) % of arithmetic mean, median, minimum, maximum, geometric mean, and CV % for the geometric mean).

Results will be displayed using 3 significant digits.

The CV % for the geometric mean will be calculated using the following formula:

$$CV (\%) = 100 * \sqrt{e^{SD^2} - 1}$$

Where SD is of the natural-log transformed data.

Figures:

Individual and mean concentration-time profiles will be provided on linear and semilogarithmic scales. For individual concentration-time profiles, the actual sampling times will be used.

Mean concentration-time profiles will be provided on linear and semilogarithmic scales and may be presented with error bars representing the Standard error of means (SEM).

12.4 Determination and Analysis of Pharmacokinetic Parameters

Full precision concentration data and actual sample times will be used for the determination of all PK parameters.

Raw plasma concentrations for the derivation of PK parameters will be handled as described in Section 12.1.

The PK parameters as listed in Section 12.1 will be estimated.

Reporting of missing PK parameters:

The percentage of extrapolated AUC should not exceed 20% of AUC_{inf} for each individual profile. If the percentage of extrapolated AUC is more than 20%, the individual AUC_{inf} result and parameters depending on AUC_{inf} will be listed but flagged as not reliably calculated. They will generally not be included in descriptive statistics and statistical testing procedures.

The terminal half-life regression analysis should contain data from at least 3 different time points after C_{max} in the terminal phase and as many data points as possible (always including the last quantifiable concentration but excluding the concentration at T_{max}), consistent with the assessment of a straight line on the log-transformed scale. The coefficient of regression (r^2) should be larger than or equal to 0.80. If at least one of these conditions is not fulfilled, the terminal half-life and parameters depending on $t_{1/2}$ will be listed but flagged as not reliably calculated. They will generally be excluded from descriptive statistics and statistical testing procedures. However, if the reliability of the estimated terminal half-life is judged to be reasonable by the pharmacokineticist who oversees the PK analysis, the $t_{1/2}$ and related parameters would not be excluded.

Individual PK parameters:

A raw data listing will be provided displaying the individual PK parameters. Results will be displayed using 3 significant digits.

Summary statistics of PK parameters:

Pharmacokinetic parameters will be summarized using descriptive statistics (n, arithmetic mean, SD, CV% for the arithmetic mean, median, minimum, maximum, geometric mean, and CV% for the geometric mean). The geometric mean and CV% for the geometric mean will not be calculated for T_{max} . Results will be displayed using 3 significant digits.

13. PHARMACODYNAMIC ENDPOINTS

Pharmacodynamic endpoints coincide with the primary and secondary efficacy endpoints. The plasma glucose profile for assessment of the primary and secondary clinical efficacy endpoints will be assessed based on plasma glucose concentration data from samples collected at the dosing visit (Visit 2).

Plasma glucose is determined at pre-dose and at 15 and 30 minutes after dosing. The actual time of blood sampling should not deviate from the nominal time by more than ± 1 minute for the collection time points. Pre-dose is defined as within 2 minutes prior to dosing.

14. SAFETY ANALYSES

All safety analyses will be based on the SAF.

14.1 Extent of Exposure

14.1.1 Diabetes Treatment prior hypoglycemia induction

A summary table will be prepared showing the number (percentage) of patients who used any of the following:

- MDI
- Insulin pump

All details related to the diabetes treatment prior hypoglycemia induction will be provided in a listing.

14.1.2 Hypoglycemia Induction Procedure

A summary table will be prepared summarizing the data collected for the hypoglycemia induction procedure. Frequency counts and percentages will be presented for the number of patients where the hypoglycemia induction procedure was performed and for the number of patients where glucose was administered intravenously prior to dosing.

The duration in minutes between stop of insulin pump (respectively for multiple daily injections (MDI) users, last basal dose before the Hypoglycaemia procedure) and time when Hypoglycaemia procedure was initiated will be calculated and summarized.

Descriptive statistics will be given for the total amount of insulin administered to induce hypoglycemia and the total amount of glucose administered during the induction procedure.

All details related to the hypoglycemia induction procedure will be provided in a listing.

14.1.3 Study Drug Administration

All data related to study drug administration will be provided in a data listing.

14.2 Local Tolerability

Local tolerability assessments at 30, 120, and 300 minutes after IMP administration will be performed to assess the following:

- Spontaneous pain
- Pain on palpation
- Itching
- Redness
- Edema
- Induration/infiltration
- Other reaction

Injection site reactions and any findings will be reported as AEs.

The analysis of local tolerability will include a summary table displaying the counts and percentages of patients experiencing local symptoms by time point, symptom and severity. Additionally, all details collected from the local tolerability assessments will be provided in a data listing. Any “other types of reaction” will be summarized under the umbrella term “Other”.

14.3 Adverse Events

Unless otherwise stated, all AE summary tables will be restricted to TEAEs, which are defined as those AEs that occurred after dosing and those existing AEs that worsened during the study. Partial dates will be imputed. For details on imputation rules, refer to Appendix A: Presentation of Data and Programming Specifications. Imputed dates are only used to determine if an AE is a TEAE: no other calculation, such as durations, will be done. If it cannot be determined whether the AE is treatment-emergent due to a partial onset date, then it will be counted as treatment-emergent. Verbatim terms in the eCRFs will be mapped to SOCs and PTs using MedDRA, version 24.1.

TEAE summaries that are displayed by SOC and PT, will be ordered by descending patient count, by SOC and PT.

Causal relationships

Causal relationship between the occurrence of an AE and the administration of the study drug is assessed by the investigator according to classification scheme: 0=not related, 1=unlikely, 2=possible and 3=probable. Probable and possible relationships will be included under the category related. All AEs must have a causal relationship assigned. In case of a missing relationship, a query will be raised in order to obtain causality assessment. In case no clarification of relationship via query is possible the missing relationship will be set to related for the analysis.

Severity

Severity grading will differ between 1=mild, 2=moderate and 3=severe. For AEs having a missing severity, the severity will not be imputed and kept as missing.

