8.3.1 Time Period and Frequency for Collecting AE and SAE Information

All AEs and SAEs will be collected from the first trial-related activity after signing of the ICF until the end of the post-treatment follow-up period (which may include contacts for follow-up of safety) at the time points specified in the SoA (Section 1.3).

All SAEs will be recorded and reported to the sponsor or designee immediately and under no circumstance should this exceed 24 hours, as indicated in Appendix 3. The investigator will provide any updated SAE data to the sponsor within 24 hours of it being available.

Investigators are not obligated to actively seek information on AEs or SAEs after conclusion of the trial participation. However, if the investigator learns of any SAE, including a death, at any time after a patient has been discharged from the trial, and he/she considers the event to be reasonably related to the trial intervention or trial participation, the investigator must promptly notify the sponsor.

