8.3.6 Hypoglycemia

Hypoglycemia will be regarded as an AE, recorded, and documented on an AE form (or SAE form, if applicable).

Since hypoglycemia will be induced during the dosing visit, in accordance with hypoglycemia clamp procedure described in Section 6.5.1, ONLY plasma glucose below 3.0 mmol/L (54 mg/dL) must be reported as an AE, at the dosing visit (Visit 2), or at instances that IV

Zealand Pharma A/S

glucose is given after IMP administration. The hypoglycemic event should be confirmed by glucose analyzer. If only the CGM device is used, the hypoglycemic event should be present for at least 15 minutes below 3.0 mmol/L for AE reporting.

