9.4.3.3 Safety and Tolerability Endpoints

Clinical Laboratory Data

Clinical laboratory test results will be marked whether the result is below, within or above the respective reference range. The number of values outside of the reference range will be counted.

AEs

AEs will be coded using the latest available version of the Medical Dictionary for Regulatory Activities. All AEs will be listed, however only AEs that are considered treatment emergent (AEs with an onset time at or after the initial dose of trial drug) will be tabulated. Such tables will include the counts and percentages of patients experiencing AEs by system organ class and preferred term. If a patient has more than 1 AE which codes to the same preferred term, the patient will be counted only once for that preferred term. The total number of events documented per system organ class and preferred term will also be displayed.

Other Safety Data

Administration and time to first IV glucose infusion, within 30 minutes after IMP administration (NB: IV glucose infusion prior to IMP administration should not be included, as it is part of hypoglycemic clamp procedure) will be described with descriptive statistics.

Vital signs, physical examination results, ECG, and local tolerability data will be summarized with descriptive statistics.

Immunogenicity

Occurrence of ADA will be analyzed descriptively. ADA and result from associated characterization assays will be presented descriptively.

Continuous Glucose Monitoring (CGM)

At Visit 2, glucose levels will be monitored by CGM.

CGM data will be presented graphically as individual plots of glucose measurements over time from the time of stopping the participant's insulin pump to 300 minutes after dasiglucagon administration.

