- Non-serious AEs: Non-serious AEs must be followed until the outcome of the event is "recovering/resolving," "recovered/resolved," or "recovered/resolved with sequelae" or until the end of the follow-up period stated in the protocol, whichever comes first, and until all queries related to these AEs have been resolved. Cases of chronic conditions, cancer, or AEs that are ongoing at time of death (where death is due to another AE) may be closed with the outcome of "recovering/resolving" or "not recovered/not resolved." Cases can be closed with the outcome of "recovering/resolving" when a patient has completed the follow-up period and is expected by the investigator to recover.

The investigator must ensure that the worst-case severity and seriousness of an event is kept throughout the trial, ie, if the severity of an AE changes over time, then it should be reported as 1 AE with the most severity. A worsening of an unresolved treatment-emergent AE must be reported as follow-up with re-assessment of severity and/or seriousness of the event. For AEs with onset before IMP administration, any worsening of severity/seriousness after IMP

Zealand Pharma A/S

Protocol ZP4207-21052 Version 6.0, 12 Jul 2024

administration should be recorded as a separate AE, with the onset date of the event corresponding to the date of the severity/seriousness upgrade.

If an AE is resolved and re-appears later then it should be reported as a new AE.

[figure not shown]
Queries or follow-up requests must be responded within 14 calendar days from the date of receipt of the request, unless otherwise specified in the follow-up request.

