14.3.1 Summary of Adverse Events

A summary table of all AEs will be prepared, summarizing the number and percentage of patients with at least 1 AE and the total number of AEs in the following categories:

1. AEs that occurred during screening
2. TEAEs
3. TEAEs occurring within 12 hours after dosing
4. TEAEs, which are AESIs
5. TEAEs, which are an other important event
6. TEAEs, which are injection site reactions based on investigator assessment on the eCRF
7. IMP related TEAEs
8. TEAEs, which are SAEs
9. IMP related TEAEs, which are SAEs
10. Deaths

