14.3 Safety Data

14.3.1 Adverse Events

**Table 14.3.1.1 Overall Summary of Adverse Events
 Safety Analysis Set**

| Adverse Event Category [n (%) m] | dasiglucagon 0.3mg (N=XX) | dasiglucagon 0.6mg (N=XX) | Total (N=XX) |
|--|------------------------------|------------------------------|-----------------|
| AEs that occurred during screening | xx (xx.x%) xx | xx (xx.x%) xx | xx (xx.x%) xx |
| Treatment-emergent adverse events (TEAEs) | xx (xx.x%) xx | xx (xx.x%) xx | xx (xx.x%) xx |
| Treatment-emergent adverse events (TEAEs) occurring within 12 hours after dosing | xx (xx.x%) xx | xx (xx.x%) xx | xx (xx.x%) xx |
| TEAEs of special interest | xx (xx.x%) xx | xx (xx.x%) xx | xx (xx.x%) xx |
| TEAEs which are other important events | xx (xx.x%) xx | xx (xx.x%) xx | xx (xx.x%) xx |
| TEAEs which are injection site reactions ^[a] | xx (xx.x%) xx | xx (xx.x%) xx | xx (xx.x%) xx |
| TEAEs which are related ^[b] to the study drug | xx (xx.x%) xx | xx (xx.x%) xx | xx (xx.x%) xx |
| Serious TEAEs | xx (xx.x%) xx | xx (xx.x%) xx | xx (xx.x%) xx |
| Serious TEAEs which are related to the study drug | xx (xx.x%) xx | xx (xx.x%) xx | xx (xx.x%) xx |
| Adverse events leading to death | xx (xx.x%) xx | xx (xx.x%) xx | xx (xx.x%) xx |

n = Number of patients; m = Number of occurrences

[a] Based on investigator assessment on the eCRF

[b] Probable and possible relationships are included under the category related. In case of missing relationship will be set to related for the analysis.

Patients reporting more than 1 event are counted only once for the patient count.

Percentages are based on the total number of patients in the safety analysis set for the given dose group.

Treatment-emergence is defined as those AEs that occurred after dosing and those existing AEs that worsened during the study.

Source: xxx

PROGRAM SOURCE: xxx.sas, DATA CUT-OFF DATE: DDMMYYYY

RUN DATE: DDMMYYYY hh:mm

Table 14.3.1.2 Treatment-Emergent Adverse Events by System Organ Class and Preferred Term
Safety Analysis Set

| System organ class Preferred term [n (%)] | dasiglucagon 0.3mg (N=XX) | dasiglucagon 0.6mg (N=XX) | Total (N=XX) |
|--|------------------------------|------------------------------|-----------------|
| Any treatment-emergent adverse events | xx (xx.x%) xx | xx (xx.x%) xx | xx (xx.x%) xx |
| System organ class 1 | xx (xx.x%) xx | xx (xx.x%) xx | xx (xx.x%) xx |
| Preferred term 1 | xx (xx.x%) xx | xx (xx.x%) xx | xx (xx.x%) xx |

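### The SAP's treatment-emergent definition does not tie worsening to dosing, and AEs starting at Visit 2 before the injection have no clear summary row

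*SAP*

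**What the plan says.** **Definition in the SAP.** SAP 14.3 states: "Unless otherwise stated, all AE summary tables will be restricted to TEAEs". It defines TEAEs as "those AEs that occurred after dosing and those existing AEs that worsened during the study". The table shells repeat the rule as a footnote: "Treatment-emergence is defined as those AEs that occurred after dosing and those existing AEs that worsened during the study". That footnote stands under Table 14.3.1.1 and every other TEAE shell (14.3.1.2, 14.3.1.3 and 14.3.1.5 to 14.3.1.10), so it is what a programmer would implement.

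**Definition in the protocol.** Protocol 9.4.3.3 lists all AEs but tabulates only treatment-emergent ones, described as "AEs with an onset time at or after the initial dose of trial drug". It has no worsening clause. SAP 15 reports no changes to the protocol-specified analysis.

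**Recording rules.** Under Protocol 8.3.1, "All AEs and SAEs will be collected from the first trial-related activity after signing of the ICF". Protocol 10.3.4 keeps an AE whose severity changes as one record at its worst severity, with one exception: "For AEs with onset before IMP administration, any worsening of severity/seriousness after IMP" administration is entered as a separate AE, with onset dated to the upgrade.

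**Pre-dose AEs in the summaries.** SAP 14.3.1 has one pre-dose category: "AEs that occurred during screening". Table 14.3.1.4 repeats it by system organ class and preferred term. SAP 7 uses the label Screening for Visit 1 and Dosing for Visit 2. Insulin induction takes place at Visit 2.

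**The concern.** A treatment-emergent count is meant to separate what happened from the injection onwards from what came before. Here the period before is not empty. Visit 2 follows screening by 4 to 7 weeks (Protocol 8.1.2), or by up to 50 + 21 = 71 days if rescheduled (Protocol 5.5), and each child then receives IV insulin to lower glucose. AEs can therefore begin, and in principle worsen, before any dasiglucagon is given. A definition that counts worsening at any time in the study blurs that line, and does so without saying that it departs from the protocol.

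The second issue is coverage. Protocol 8.3.6 makes plasma glucose below 3.0 mmol/L (54 mg/dL) at the dosing visit a reportable AE, so events during induction are foreseeable. If they are neither screening AEs nor treatment-emergent, a table introduced as a summary of all AEs leaves out events of the trial procedure. With 4 children per dose, a single event is visible in the percentages.

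**Working it through.** No design figure depends on this rule, so the check sets the passages side by side and follows each kind of AE through them.

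| Kind of AE | Protocol 9.4.3.3 with 10.3.4 | SAP 14.3 and 14.3.1, read literally |
|---|---|---|
| A. New onset after injection | Treatment-emergent | TEAE (occurred after dosing) |
| B. Pre-dose onset, worsens after injection | Separate AE dated to the upgrade, so treatment-emergent | TEAE already, through the new record |
| C. Pre-dose onset, worsens before injection | One record with pre-dose onset, not treatment-emergent | TEAE through the worsening clause; also in category 1 if onset was during screening |
| D. Onset before Visit 2, no worsening | Not treatment-emergent; listed | Category 1 |
| E. Onset at Visit 2 before IMP, no worsening | Not treatment-emergent; listed | Not a TEAE; in category 1 only if screening extends to the injection |

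**Row B.** If sites follow Protocol 10.3.4, post-dose worsening is already a new AE with post-dose onset, and the first half of the SAP definition captures it. The worsening clause then adds little beyond row C. Its other possible use is as a safety net where a site did not open the separate record, or dated the upgrade on Day 1 without a time. Wording tied to the injection would serve that purpose too.

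**Row C.** This is the conflict between the documents. How often it could occur depends on what the data hold. Protocol 10.3.4 keeps such an AE as one record at worst severity, and the minimum AE fields in Protocol 10.3.3 include onset and resolution times but no time of worsening. A program would seldom have a variable that shows pre-dose worsening.

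**Row E.** The result depends on when screening ends, which the SAP does not state. With screening read as Visit 1 (SAP 7), or as the period before Visit 2, these AEs are in neither category 1 nor category 2. Categories 3 to 9 are subsets of TEAEs, so they do not help. Only the death row is not restricted to TEAEs. A non-fatal serious AE during induction, in a child who is then dosed, would appear in listings but in no AE summary row. With screening read as everything before IMP, row E falls in category 1.

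**Weight of one child.** SAP 4 gives 4 children per dose and 8 in total.

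- Dose group: 1/4 = 25.0 percentage points.
- Total: 1/8 = 12.5 percentage points.

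This is the weight of any single child, not an estimate of how many would be misclassified.

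**The case against.** The strongest reply is that the clause has almost nothing to act on. The only worsening that creates its own record is worsening after IMP, which is properly treatment-emergent, and the clause can be read as a loose restatement of that rule. This stands as a limit on the effect. It does not make the wording agree with Protocol 9.4.3.3.

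On induction AEs, the reply is that SAP 7 gives visit labels rather than AE periods, and that the protocol requires pre-dose AEs to be listed, not tabulated. Listing 16.2.7.1 carries start time, a hypoglycemia flag and the glucose value. IV glucose before dosing is tabulated (SAP 14.1.2), and analyzer glucose is summarized (SAP 14.10). With 8 children and no inferential testing, a reader can review the listing. This also stands: nothing is lost from the record. But the SAP chose to tabulate some pre-dose AEs without saying where that category ends.

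Three stronger readings are tempting and are not supported:

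- *Pre-dose worsening is attributed to dasiglucagon.* Treatment-emergent is a class defined by timing. The related tables need an investigator rating of possible or probable, or a rating still missing after query.
- *The AESI table would fill with induction events.* Protocol 8.3.5 defines both kinds of AESI as post-dose.
- *Induction AEs certainly fall in no table.* That holds only if screening stops before Visit 2.

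**Conclusion.** The SAP's classification rule conflicts with the protocol's and the difference is not declared. Taken literally, it places pre-dose worsening under a dasiglucagon column as treatment-emergent. Provided sites record AEs as Protocol 10.3.4 directs, few if any records would be misclassified. Separately, AEs with onset at Visit 2 before IMP have no clear summary row; if screening means Visit 1, the non-fatal ones have none. Either error, if it occurred in one child, would move a dose-group percentage by 25 points and the total by 12.5 points. The primary endpoint, the sample size and the confidence intervals are untouched. This is worth correcting because the rule is explicit, the documents disagree, and the change is simple.

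**What to change.** 1. In SAP 14.3 and the nine TEAE shell footnotes, define a TEAE as an AE with onset, or an existing AE with worsening, at or after the time of IMP injection.
2. Redefine category 1 in SAP 14.3.1 and Table 14.3.1.4 as AEs with onset before IMP, covering screening and Visit 2 before dosing, including insulin induction. Each AE is then either pre-IMP or treatment-emergent, and categories 3 to 9 remain subsets of TEAEs. If a site did not split a pre-dose AE that worsened after injection, class that record as treatment-emergent only.
3. In SAP 15, record what still differs from Protocol 9.4.3.3: the explicit worsening clause and the tabulation of pre-IMP AEs.

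The cost is wording and minor programming. Date and time of AE onset are already collected (Protocol 10.3.3), and so is the dosing time, so no new data are needed.
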